5.5.5. Criteria to Resume Treatment

Subjects may resume treatment with GS-1423 when drug-related AE(s) resolve(s) to Grade 1 or baseline value, with the following exceptions:

- Subjects may resume treatment in the presence of Grade 2 fatigue.

- Subjects with combined Grade 2 AST/ALT **and** total bilirubin values lasting > 7 days meeting discontinuation parameters (Section 5.5.6) should have treatment permanently discontinued.
- Drug-related Grade 2 pulmonary toxicity or colitis must have resolved to baseline before treatment is resumed.
- Drug-related endocrinopathies adequately controlled with only physiologic hormone replacement may resume treatment. (Exception: Study treatment does not need to be delayed/interrupted for subjects who experience immune-related hypothyroidism [Grades 1-2].)
- Subjects who received systemic corticosteroids for management of any drug-related toxicity must be off corticosteroids or have tapered down to an equivalent dose of prednisone \leq 10 mg/day.

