Transient (\leq 3 days) Grade 3 fatigue, local reactions, headache, nausea, emesis, or diarrhea that are controlled with medical management and/or resolves to Grade \leq 1
Transient (\leq 3 days) Grade 3 flu-like symptoms or fever, which are controlled with medical management
An event clearly associated with the underlying disease, PD, a concomitant medication, or comorbidity.

Dosing/procedures-related toxicities

- Inability to receive the first 2 doses of GS-1423 because of related toxicity, even if the toxicity does not meet DLT criteria defined above (regardless of dosing schedule)

Note: Exceptions include DLT exclusions mentioned above.

- Greater than a 2-week delay in starting the next cycle of therapy due to a treatment-related toxicity, even if the toxicity does not meet the DLT criteria determined above

Grade 5 event (ie, death)

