5.5.2. Treatment Delay

For infusion-related reactions and immune-related AEs attributed to GS-1423, please follow Sections [5.5.3](#) and [5.5.4](#), respectively, for treatment delay guidance. For AEs attributed to mFOLFOX6, please follow [Appendix 6](#) for guidance.

Study treatment may also be delayed due to any AE, laboratory abnormality, or intercurrent illness which, in the judgment of the investigator, warrants a delay.

If an AE is attributed to only one study drug, it is at the Investigator's discretion to determine if the study drug(s) not attributed to the AE will be withheld based on the Investigator's assessment of risk-benefit of withholding one or more study drugs.

Subjects who have drug-related toxicities that meet the criteria for dose delay should have study drug treatment delayed until criteria to resume treatment are met. It is recommended to restart study drug treatment at the next scheduled administration.

Note: GS-1423 should be discontinued in subjects who experience any Grade ≥ 3 skin drug-related AE, suspected/confirmed Stevens-Johnson syndrome, or suspected/confirmed toxic epidermal necrolysis. See Section [5.5.6](#) for permanent treatment discontinuation criteria due to AEs.

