5.5.4.2. Gastrointestinal irAEs

Rule out non-inflammatory causes. If a non-inflammatory cause is identified, treat accordingly and continue therapy. Opiates/narcotics may mask symptoms of perforation. Infliximab should not be used in cases of perforation or sepsis.

Table 5-4. Gastrointestinal irAE Management Algorithm

| Gastrointestinal irAEs | | |
|--|--|---|
| CTCAE Grade of Diarrhea / Colitis | Management | Follow-up |
| Grade 1 Diarrhea: < 4 stools/day over baseline. Colitis: asymptomatic. | Continue GS-1423 therapy per protocol. Symptomatic treatment. | Close monitoring for worsening symptoms. Educate subject to report worsening immediately. Consider symptomatic treatment including hydration, electrolyte replacement, dietary changes (eg, American Dietetic Association colitis diet), and loperamide. If worsens: Treat as Grade 2 or 3-4. |
| Grade 2 Diarrhea: 4-6 stools per day over baseline; IV fluids indicated < 24 h; not interfering with activities of daily living (ADL). Colitis: abdominal pain; blood in stool. | Delay GS-1423 therapy per protocol. Symptomatic treatment. | If improves to Grade 1: Resume GS-1423 therapy per protocol. If persists > 5 to 7 days or recurs: 0.5-1 mg/kg/day methylprednisolone or equivalent. When symptoms improve to Grade 1, taper corticosteroids over \geq 1 month; consider prophylactic antibiotics for opportunistic infections; resume GS-1423 therapy per protocol. If worsens or persists > 3 to 5 days with oral corticosteroids: Treat as Grade 3-4. |
| Grade 3-4 Diarrhea (Grade 3): \geq 7 stools per day over baseline; incontinence; IV fluids \geq 24 h; interfering with ADL. Colitis (Grade 3): severe abdominal pain, medical intervention indicated, peritoneal signs. Grade 4: life-threatening, perforation | Discontinue GS-1423 therapy per protocol. 1-2 mg/kg/day methylprednisolone IV or equivalent. Add prophylactic antibiotics for opportunistic infections. Consider lower endoscopy. | If improves: Continue corticosteroids until Grade 1, then taper over \geq 1 month. If persists > 3 to 5 days or recurs after improvement: Add infliximab 5 mg/kg (if no contraindication). Note: Infliximab should not be used in cases of perforation or sepsis. |

ADL activities of daily living; CTCAE Common Terminology Criteria for Adverse Events; irAE immune related adverse event; IV intravenous.

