5.6.1.1. Rescue Medications and Supportive Care

Subjects should receive appropriate supportive care measures as deemed necessary by the treating investigator including but not limited to the items outlined below.

For guidelines for continuing treatment with GS-1423, see Section [5.5.5](#).

- **Diarrhea:** Subjects should be carefully monitored for signs and symptoms of enterocolitis (such as diarrhea, abdominal pain, blood or mucus in stool, with or without fever) and of bowel perforation (such as peritoneal signs and ileus). In symptomatic subjects, infectious etiologies should be ruled out, and if symptoms are persistent and/or severe, endoscopic evaluation should be considered. All subjects who experience diarrhea should be advised to drink liberal quantities of clear fluids or rehydration solutions. If sufficient oral fluid intake is not feasible, fluid and electrolytes should be substituted via IV infusion.
- **Anemia:** Transfusions may be utilized as clinically indicated for the treatment of anemia but should be clearly noted as concurrent medications or in a transfusion page. Consider a potential immunologic etiology and follow the American Society of Clinical Oncology (ASCO) guidelines for use of erythropoietin or derivatives.
- **Neutropenia:** Prophylactic use of colony-stimulating factors including granulocyte colony-stimulating factor (G-CSF), PEGylated G-CSF, or granulocyte macrophage colony-stimulating factor is not allowed in this study. Therapeutic use of G-CSF is allowed in subjects with Grade 3 to 4 febrile neutropenia. Consider a potential immunologic etiology.

- Thrombocytopenia: Transfusion of platelets may be used if clinically indicated. Immune thrombocytopenia purpura should be ruled out before initiation of platelet transfusion.
- Anti-infectives: Subjects with suspected or documented infectious complication should receive oral or IV antibiotics or other anti-infective agents as considered appropriate by the treating investigator for a given infectious condition, according to standard institutional practice.

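### Table 5-4 lets sites resume GS-1423 once Grade 2 colitis improves to Grade 1, while Section 5.5.5 requires return to baseline

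*Protocol*

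**What the plan says.** Protocol Section 5.5.5 sets the conditions for restarting GS-1423 after a drug-related adverse event. The general rule is resolution to Grade 1 or to the baseline value. A list of exceptions follows, one of which reads "Drug-related Grade 2 pulmonary toxicity or colitis must have resolved to baseline before treatment is resumed". For Grade 2 colitis, therefore, Grade 1 is not enough.

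Table 5-4 in Section 5.5.4.2 grades diarrhea and colitis in the same rows, and its Grade 2 row includes colitis with abdominal pain or blood in the stool. The follow-up column has two routes back to treatment:

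- Without steroids: "If improves to Grade 1: Resume GS-1423 therapy per protocol".
- With steroids, if the event recurs or lasts beyond 5 to 7 days: "When symptoms improve to Grade 1, taper corticosteroids over" at least 1 month, and then resume.

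Neither route states a baseline condition for colitis or cites Section 5.5.5.

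The cross-references point both ways. Section 5.5.2 says "For infusion-related reactions and immune-related AEs attributed to GS-1423, please follow Sections" 5.5.3 and 5.5.4 respectively, and Section 5.5.4 contains Table 5-4. The same section then says that subjects whose drug-related toxicity calls for a delay "should have study drug treatment delayed until criteria to resume treatment are met". Section 5.6.1.1 says "For guidelines for continuing treatment with GS-1423, see Section" 5.5.5.

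**The concern.** The baseline exception exists because the sponsor judged Grade 1 insufficient for colitis. Table 5-4 then applies the general Grade 1 rule to that same event.

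Table 5-4 describes Grade 1 colitis as asymptomatic. A subject whose symptoms have cleared but whose colitis has not returned to baseline would be re-dosed under the table and held under Section 5.5.5. This is a first-in-human study (Section 1.2.3). Section 7.1.2.1 names colitis among the events needing particular attention, and Table 5-10 requires permanent discontinuation at Grade 3 or higher. Re-dosing too early therefore carries a real risk.

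There is a secondary link to dose escalation. One of the DLT criteria in Section 3.2.3.3 is "Inability to receive the first 2 doses of GS-1423 because of related toxicity". Two sites using different thresholds could record the same course of colitis differently.

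**Working it through.** **Comparing the two rules.** All events are Grade 2 and drug-related.

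| Situation | Section 5.5.5 | Table 5-4 | Result |
|---|---|---|---|
| Diarrhea without colitis | Grade 1 or baseline | Grade 1 | Agree |
| Colitis, no steroids | Baseline | Grade 1 | Conflict |
| Colitis, steroids given | Baseline, and off steroids or at most 10 mg/day prednisone equivalent | Grade 1 starts a taper of at least 1 month, then resume | Baseline condition missing |
| Colitis, subject's own baseline is Grade 1 | Grade 1 | Grade 1 | Coincide |

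The direct conflict is in the second line. In the steroid route, Grade 1 triggers the taper and not the drug, so the defect there is a missing condition and matters less.

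**Could a reader take the Grade 1 trigger as deliberate?** Yes. The Grade 2 rows of Table 5-6 (hepatic, steroid-free route) and Table 5-9 (neurological) name return to baseline as the point for resuming. Where those tables want baseline, they say so.

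**Table 5-5 (pulmonary).** In its Grade 2 row, near-baseline symptoms start a taper of at least 1 month, and treatment resumes afterwards. The row does not repeat the baseline requirement of Section 5.5.5. This is an omission, not a contradiction.

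**Timing against the DLT window.** Inputs: Part A doses every 2 weeks from Day 1, the window is 28 days (Section 3.2.3.1), and on restarting Section 5.5.2 says "It is recommended to restart study drug treatment at the next scheduled administration".

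- Dose 2 due: Day 1 + 14 = Day 15.
- Next scheduled slot if dose 2 is held: 15 + 14 = Day 29.
- Days past the window: 29 − 28 = 1.
- First day on which the delay exceeds 2 weeks: 15 + 14 + 1 = Day 30.

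A subject at Grade 1 but not at baseline on Day 15 receives dose 2 under Table 5-4. Under Section 5.5.5 the dose is held. If it is then given at the next scheduled slot, it falls on Day 29, and the subject could count as unable to receive the first 2 doses. The separate DLT criterion for a delay of more than 2 weeks cannot be met for dose 2 inside the window, because Day 30 is later than Day 28.

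**Discontinuation limit.** Section 6.10.1 stops treatment after more than 4 weeks without GS-1423 on this schedule. A gap from Day 1 to Day 29 is 28 days, exactly 4 weeks, and does not exceed the limit. Holding a further dose moves the next slot to 29 + 14 = Day 43, a gap of 42 days, which does.

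**The case against.** The strongest reply is that the protocol already resolves the conflict. Table 5-4 qualifies its instruction by reference to the protocol, and the protocol's rule for resuming is Section 5.5.5, whose exception is mandatory. Section 5.5.4 presents the algorithms as an aid to investigators. Sections 5.5.2 and 5.6.1.1 both lead back to the resume criteria. On this reading only a cross-reference is missing. It is the better legal reading, but it does not remove the stated Grade 1 trigger, and Section 5.5.2 also directs sites to these tables.

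Four further points limit the consequence, and they stand:

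- Once colitis is asymptomatic, Grade 1 and baseline may often look alike in the clinic. The steroid-free route is also short, since persistence beyond 5 to 7 days leads to steroids.
- In the steroid route, a taper of at least 1 month will often run into the 4-week discontinuation limit, unless dosing restarts once prednisone is at 10 mg/day or below.
- Restarting at the next scheduled slot is only recommended. Footnotes b and w of the Q2W/Q3W procedures table in Appendix 2 allow visits to be delayed and later ones adjusted. A subject back at baseline on Day 18, for example, could receive dose 2 inside the window. The Day 29 case is therefore conditional.
- SAP Section 1 records that the study ended at completion of Part A, so little or no future dosing under this protocol is affected.

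**Conclusion.** The concern holds. For drug-related Grade 2 colitis, Table 5-4 and Section 5.5.5 give different thresholds for re-dosing, and the table's is the less protective.

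The effect is small in scope. It is confined mainly to colitis managed without steroids in subjects whose baseline is below Grade 1, and it needs a dose to fall due while the subject is at Grade 1 but not yet at baseline. The documents give no rate for this, so no expected number of subjects can be stated. The main consequence is for patient safety. The DLT consequence depends on dose 2 being held on Day 15 and restarted at the next scheduled slot. No sample size, error rate or planned analysis is affected.

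The correction should still be made, because a stated dosing rule contradicts the protocol's own mandatory criterion. The Table 5-5 point is a clarification and would not justify a change alone.

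**What to change.** Split the Grade 2 row of Table 5-4:

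- Grade 2 diarrhea without colitis: resume at Grade 1.
- Grade 2 colitis: resume only at baseline, with or without steroids, citing Section 5.5.5.

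At the same time, add to the Grade 2 row of Table 5-5 that GS-1423 resumes after the taper only if the pulmonary toxicity has resolved to baseline, again citing Section 5.5.5.

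The cost is protocol wording only: one table row and one phrase. No procedure, visit or analysis is added. With the study closed after Part A, the practical value lies mostly in any later protocol that reuses these algorithms.

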5.5.6. Permanent Treatment Discontinuation

Study drug treatment must be discontinued for drug-related AEs described in [Table 5-10](#). Non-AE reasons for study treatment discontinuation can be found in Section [6.10.1](#).

Table 5-10. Drug-Related Adverse Events Requiring Discontinuation of GS-1423

| Toxicity Category* | Qualifying Severity/Duration |
|--------------------|--|
| Ophthalmic | 
• Grade 2 uveitis, blurred vision, eye pain, and/or reduction of visual acuity that does not respond to topical therapy and does not improve to Grade 1 severity within 2 weeks OR requires systemic treatment• Grade 3 or higher uveitis |
| Gastrointestinal | 
• Grade 3 or higher diarrhea, colitis |
| Neurologic | 
• Grade 3 or higher neurologic toxicities |
| Dermatologic | 
• Grade 3 or higher skin AE, suspected Stevens-Johnson syndrome, or toxic epidermal necrolysis |
| Pulmonary | 
• Grade 2 pneumonitis or interstitial lung disease that does not improve after 2 weeks or worsening despite dose delay and systemic corticosteroids (see Table 5-5)• Grade 3 or higher pneumonitis |
| Endocrinopathies | 
• Grade 3 endocrinopathies not adequately controlled with physiologic hormone replacement• Grade 4 or higher endocrinopathies |
| Hypersensitivity | 
• Grade 3 or higher bronchospasm, hypersensitivity reaction, or infusion-related reaction |

| Toxicity Category* | Qualifying Severity/Duration |
|--------------------|--|
| Laboratory | 
Thrombocytopenia
 
• Grade 3 thrombocytopenia lasting > 7 days or associated with clinically significant bleeding (i.e. requires hospitalization, transfusion of blood products, or other urgent medical intervention)• Grade 4 thrombocytopenia 
Neutropenia
 
• Grade 4 neutropenia lasting > 7 days 
Electrolyte Abnormalities
 
• Grade 4 electrolyte abnormalities with clinical sequelae• Grade 4 electrolyte abnormalities unable to be corrected with supplementation/appropriate management within 72 hours of onset 
Liver Function Abnormalities (see Table 5-6)
 
• AST or ALT > 5 × ULN• Total bilirubin > 3 × ULN• Concurrent AST or ALT > 3 × ULN AND total bilirubin > 2 × ULN lasting > 7 days |
| Other | 
• Grade 2 or 3 adverse event (laboratory or non-laboratory) that does not resolve in ≤ 12 weeks• Recurrence of Grade 3 or higher adverse event (laboratory or non-laboratory)• Grade 4 non-hematologic adverse event |

* AE must be study drug related for discontinuation reasons to apply

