3.2.3.3. Definition of Dose Limiting Toxicity

Toxicity will be graded according to National Cancer Institute Common Terminology Criteria for Adverse Events Version 5.0 (NCI CTCAE v5.0). A DLT is a toxicity observed in the first 28 days as defined below and considered possibly related to GS-1423.

A DLT may lead to permanent withdrawal of GS-1423 for the subject after discussion between the Investigator and Gilead.

Hematologic

- Grade 3 thrombocytopenia with clinically significant bleeding (ie, requires hospitalization, transfusion of blood products, or other urgent medical intervention)
- Grade ≥ 3 febrile neutropenia (absolute neutrophil count [ANC] $< 1.0 \times 10^9/L$ and fever $> 101^{\circ}\text{F}/38.3^{\circ}\text{C}$)
- Any Grade 4 hematologic laboratory abnormalities/AEs regardless of duration will be considered DLTs with the **exception** of

Grade 4 lymphopenia

Grade 4 neutropenia lasting ≤ 7 days that is not associated with fever (the use of growth factors is permitted)

Grade 4 anemia explained by underlying disease

Non-Hematologic

- Grade 4 non-hematologic (laboratory and non-laboratory) AEs will be considered DLT regardless of the duration
- Any \geq Grade 2 uveitis, blurred vision, eye pain, and/or reduction of visual acuity that does not respond to topical therapy and does not improve to Grade 1 severity within 2 weeks of the initiation of topical therapy OR requires systemic treatment will be considered as a DLT
- The following Grade 3 non-hematologic AEs **will be considered as DLTs**:

Any Grade 3 AE of unknown etiology consistent with an immune phenomenon that does not resolve to \leq Grade 1 or to baseline with immunosuppressive therapy within 3 weeks of its onset

Any Grade 3 central nervous system (CNS)-related AE of unknown etiology consistent with an immune phenomenon regardless of duration or reversibility

Alanine aminotransferase (ALT) or aspartate aminotransferase (AST) elevation $\geq 3 \times$ upper limit of normal (ULN), also showing elevation of serum total bilirubin of $> 2 \times$ ULN, without initial findings of cholestasis (elevated serum alkaline phosphatase)

- Any other non immune-related Grade 3 AE **except:**

Any Grade 3 endocrinopathy that is adequately controlled by hormonal replacement
Grade 3 AE of tumor flare (defined as local pain, irritation, or rash localized at sites of known or suspected tumor)

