5.5.4. Management of Potential Immune-Related Adverse Events

Immune-related AEs may be associated with immuno-oncology agents such as GS-1423 and will be categorized as AEs of interest in this study. An irAE is defined as an AE of unknown etiology, that is potentially associated with study drug exposure and is consistent with an immune-mediated phenomenon. Efforts should be made to rule out other etiologies prior to labeling an AE of clinical interest. Early recognition and management of irAEs may mitigate

severe toxicity. Investigators should also monitor subjects closely for potential irAEs, which may manifest after weeks of treatment, at the earliest. Such events may consist of persistent rash, diarrhea, colitis, autoimmune hepatitis, pneumonitis, encephalitis, arthritis, glomerulonephritis, cardiomyopathy, or uveitis and other inflammatory eye conditions.

Management algorithms have been developed to assist investigators in assessing and managing the following groups of irAEs: dermatological, gastrointestinal, pulmonary, hepatic, endocrine renal, and neurological, among others.

Adverse events (both non-serious and serious) associated with drug exposure and consistent with an immune phenomenon may represent an immunologic etiology. These irAEs may be predicted based on the nature of the study drugs, their mechanism of action, and reported experience with immunotherapies that have a similar mechanism of action. An irAE can occur any time from shortly after the first dose to several months after the last dose of treatment. Particular attention should be paid to AEs that may be suggestive of potential irAEs, as outlined below.

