- Dose delay of GS-1423 which results in no GS-1423 dosing for more than 4 weeks (QW or Q2W) or 6 weeks (Q3W)
- Discontinuation of the study at the request of Gilead, a regulatory agency, or an IRB/IEC
- Any AE and/or laboratory abnormality in the judgment of the investigator, presents a substantial clinical risk to the subject with continued treatment
- AEs specifically described in Section [5.5.6](#) must lead to study drug discontinuation.

NOTE: Tumor flare phenomenon, defined as local pain, irritation, or rash localized at sites of known or suspected tumor does not require treatment discontinuation.

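### Table 5-10 makes treatment-resistant blurred vision, eye pain or reduced visual acuity a mandatory stop at Grade 2 but not at Grade 3

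*Protocol*

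**What the plan says.** Discontinuation is mandatory for the drug-related events listed in Table 5-10 (Protocol 5.5.6). The Ophthalmic row has two bullets.

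- The first applies at Grade 2, with no wording that extends it upward. It covers uveitis, blurred vision, eye pain and reduced "visual acuity that does not respond to topical therapy and does not improve to Grade 1 severity within 2 weeks OR requires systemic treatment".
- The second is "Grade 3 or higher uveitis". It does not name the other three events.

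The DLT definition in 3.2.3.3 lists the same four events with almost the same trigger, but from Grade 2 upward: an event that does not settle within 2 weeks "of the initiation of topical therapy OR requires systemic treatment will be considered as a DLT". That section says only that a DLT may lead to withdrawal, after discussion with the sponsor.

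On resumption, section 5.5.5 states: "Subjects may resume treatment with GS-1423 when drug-related AE(s) resolve(s) to Grade 1 or baseline value, with the following exceptions". None of the exceptions is ophthalmic. It adds a steroid condition: "Subjects who received systemic corticosteroids for management of any drug-related toxicity must be off corticosteroids or have tapered down to an equivalent dose" of prednisone no higher than 10 mg/day. Section 6.10.1 requires a stop once GS-1423 has not been given for more than 4 weeks (QW or Q2W) or 6 weeks (Q3W).

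**The concern.** A mandatory stopping rule should not become more lenient as the event gets worse. Read literally, a subject with Grade 2 loss of acuity that resists topical therapy is permanently off drug. A subject with Grade 3 loss of acuity and the same course may be held and re-dosed. Section 5.5.4 names uveitis and other inflammatory eye conditions among the potential immune-related events, so this kind of event is foreseeable. What is at stake is re-exposure to the drug after a severe sight-related reaction. Sample size, error rates and the planned analyses are not affected.

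**Working it through.** The plan gives no figure to reproduce. The check compares the rules by grade and then measures how long the opening lasts.

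**1. Outcome by grade**, for a first drug-related event that fails topical therapy at 2 weeks or needs systemic treatment:

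| Grade | Uveitis | Blurred vision, eye pain, reduced acuity |
|---|---|---|
| 2 | Mandatory stop (Ophthalmic, first bullet) | Mandatory stop (Ophthalmic, first bullet) |
| 3 | Mandatory stop (Ophthalmic, second bullet) | No stop at this trigger |
| 4 | Mandatory stop | Mandatory stop (Other row, Grade 4 non-hematologic) |

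**2. Could another rule supply the missing Grade 3 stop?**

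- *Table 5-10, Other row.* It reaches a Grade 3 event only if the event is unresolved at 12 weeks or recurs. A first event that recovers is not caught.
- *DLT definition (3.2.3.3).* It covers Grade 3, but withdrawal is optional and the DLT window is 28 days. Treatment may run for 1 year.
- *Immune-related algorithms (5.5.4).* They are introduced as covering "groups of irAEs: dermatological, gastrointestinal, pulmonary, hepatic, endocrine renal, and neurological, among others". Tables 5-3 to 5-9 include no eye table. The pulmonary row of Table 5-10 has a similar two-bullet form, but Table 5-5 separately directs discontinuation at Grade 3-4. Eye events have no such second rule.
- *Dosing-gap limit (6.10.1).* It stops only subjects who do not recover in time.

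**3. How long is the opening?** Assumptions: last dose on day 0; onset on day d, before the next scheduled dose; topical therapy starts at onset; topical failure is declared 14 days later; the gap is counted from the last dose; visit windows are ignored.

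- Topical failure: day d + 14.
- Last permitted re-dose: day 28 on QW and Q2W, day 42 on Q3W. Both fall on scheduled dosing days, which fits the advice in 5.5.2: "It is recommended to restart study drug treatment at the next scheduled administration".
- Q2W (Part A): 28 − (d + 14) = 14 − d. For d = 0 to 13 this is 14 down to 1 day.
- QW: 28 − (d + 14) = 14 − d. For d = 0 to 6 this is 14 down to 8 days.
- Q3W: 42 − (d + 14) = 28 − d. For d = 0 to 20 this is 28 down to 8 days.

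A Grade 3 event that reaches Grade 1 in this time, with any systemic steroid stopped or down to 10 mg/day of prednisone or less, may be re-dosed. At Grade 2 the stop is already final on day d + 14. A later start of topical therapy shortens the time. Where the trigger is a need for systemic treatment, the Grade 2 stop does not wait 2 weeks. The interval to the last permitted re-dose can then be longer, but the taper condition applies.

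**The case against.** The strongest opposing case is that very few subjects could be re-dosed through this gap.

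- **Steroid taper.** A Grade 3 event that has failed topical therapy is likely to need systemic steroids. The tapers directed in 5.5.4 run for at least 1 month. With 14 − d days left on Q2W, few such subjects would be down to 10 mg/day in time. This stands as a limit on size. It does not exclude re-dosing, because 10 mg/day can be reached before a taper ends, and some events recover without systemic steroids.
- **Corticosteroid restriction.** Section 5.6.2 says treatment will be discontinued in subjects who need corticosteroids. Its exceptions are premedication, local routes and prednisone up to 10 mg/day. Yet 5.5.5 foresees resuming after a taper, and 6.10.1 requires a stop only when more than 10 mg/day is needed for more than 6 weeks. These sections do not agree, so for the systemic-treatment trigger the protocol is unclear rather than plainly open. The topical-failure trigger is unaffected, since topical and intraocular steroids are allowed.
- **Other stops.** Visual loss classed as neurologic would meet the Grade 3 neurologic row. Section 6.10.1 also requires a stop for any event that the investigator judges a substantial clinical risk. Both narrow the group, but they rest on classification or judgment, and Table 5-10 exists to make some stops automatic.
- **Reading of the trigger.** The first limb needs both no response and no improvement to Grade 1, so a partial responder may not meet it at any grade. Conversely, a Grade 3 event that has fallen to Grade 2 by 2 weeks might be read into the Grade 2 bullet. The text does not say so, and a mandatory stop should not depend on that inference.
- **Early termination.** SAP section 1 says Part B and Phase 1b will not be initiated. The QW and Q3W figures therefore describe schedules that were not run, and only the Q2W figure bears on this study.

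**Conclusion.** The point holds: the rule is wrong as written. For blurred vision, eye pain and reduced acuity, the mandatory stop exists at Grades 2 and 4 but not at Grade 3 on the same trigger, and no other section reliably fills the gap. Because the DLT definition applies the same trigger from Grade 2 upward, this looks like a drafting omission.

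The exposed group is narrow: a first, drug-related, non-uveitis Grade 3 eye event that fails topical therapy or needs systemic treatment, yet recovers and meets the steroid condition before the dosing-gap limit. On Q2W the opening after topical failure is 1 to 14 days under the assumptions above. The documents give no basis for a count of subjects. The severity is minor, because the group is small and the study ended after Part A.

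**What to change.** Change the first ophthalmic bullet of Table 5-10 to read Grade 2 or higher for all four events, so that it matches 3.2.3.3. Keep the second bullet, so that Grade 3 or higher uveitis remains an unconditional stop. As the study ended after Part A, apply the change to any subject still on treatment and to any later protocol that reuses the table. The cost is a wording change to one bullet. It needs no extra procedures, visits or subjects.
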